12.3 Treatment Assignment Procedures

12.3.1 Assignment Procedures

Cohorts 1 and 2 will be enrolled sequentially following dose-escalation rules. Two sentinels in each cohort will be observed for 72 hours for safety in each dose cohort. If no halting rules are met after the 2 sentinels in each cohort have been observed for 72 hours after study vaccination, the remaining 8 volunteers will be enrolled in each cohort.

The dose for Cohorts 3, 4, and 6 was selected from Cohorts 1 and 2 after evaluation of reactogenicity, safety, and initial immunogenicity. Dose selection will be determined by the Gritstone clinical team in consultation with the PI(s). Cohorts 3, 4, and 6 will be enrolled in parallel. There will be no sentinel dosing in Cohorts 3, 4, and 6.

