7.2. Study Vaccine Administration

Depending on the Cohort, study vaccination will be comprised of one or two intramuscular (IM) injections in the deltoid muscle of the subject's preferred arm. For Cohorts 1 and 2, initially subjects began the study only planning to receive one dose. In order to receive a booster dose, each subject needed to sign another ICF.

The number of doses received will be summarized for the SAF using descriptive statistics for qualitative variables. In addition, the vaccine administration data will be presented in a data listing.

8. Efficacy and Immunogenicity Analysis

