8.1. Efficacy analysis

COVID-19 incidence in subjects will be assessed using two separate metrics. The number and percentage of subjects who had (1) a positive nasal swab SARS-CoV-2 PCR test during the study and (2) an Adverse Event with a MedDRA preferred term of "COVID-19", "Asymptomatic COVID-19", or "COVID-19 pneumonia" will be summarized for the SAF.

For both measures, the incidence rate (IR) is defined as the number of subjects with an event divided by the number of subjects at risk and person-days adjusted by person-years (total time at risk). The IR's of subjects with (1) positive PCR and (2) MedDRA preferred terms indicating COVID-19 will be reported in the fashion of 100 person-years (see the [formula below](#)).

$$IR = \frac{\text{number of subjects with positive PCR}}{\text{sum(Person - days at risk)}} * 365.25 * 100$$

Person-Days at risk are defined as the total time from injection date of prime dose to the date of the positive PCR test for (1) or AE start date for (2), last date of study participation, data cutoff date, whichever is the earliest. The respective 95% CIs of positive nasal swab SARS-CoV-2 PCR tests and COVID-19-related adverse events will be calculated using the Clopper-Pearson [6] method.

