Only TEAEs will be included in summary tables and will be summarized by cohort and vaccination (Vaccination Dose 1, Vaccination Dose 2, entire study period). Percentages will be based upon the number of participants in the Safety Analysis Set within each cohort. A subject may have more than 1 AE for an SOC or PT. A subject with 2 or more AEs within the same level of summarization will be counted only once in that level 1

The rules described in [Table 4](#) will be applied for AEs partial dates during this study to understand if it is TEAE. No other data will be imputed.

All AEs will be reported by data listings for the SAF.

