9.1.1. Unsolicited Adverse Events

Unsolicited non-serious AEs will be captured for 28 days following each GRT-R910 vaccination. Unsolicited adverse events may be recorded beyond 28 days, but only AEs occurring within 28 days of treatment vaccination will be summarized. In addition, SAEs and AESIs, including PIMMCs, MAAEs, and NOCMCs, will be captured throughout the entire study following GRT-R910 vaccination. Incidence of Unsolicited Adverse Events

An overall summary of unsolicited TEAEs through 28 days after GRT-R910 vaccination (1st dose and/or booster dose) including the number and percentage of subjects who experienced the following will be presented:

- Any unsolicited TEAEs
- Any unsolicited Treatment-Related TEAEs

- Any serious TEAEs
- Any serious Treatment-Related TEAEs
- Any unsolicited severe TEAEs
- Any Treatment-Related severe TEAEs
- Any unsolicited AESIs

An overall summary of the following AEs will be presented throughout the entire study:

- Any serious AEs
- Any unsolicited medically attended TEAEs (MAAEs)
- Any unsolicited AESIs: severe COVID-19
- Any unsolicited AESIs: PIMMCs
- Any unsolicited AESIs: NOCMs
- Any unsolicited AESIs: Serologically or Virologically Events Confirmed Relevant to COVID-19
- Any Treatment-Related AEs
- Any Treatment-Related MAAEs
- Any Treatment-Related unsolicited AESIs: severe COVID-19
- Any Treatment-Related AESIs: PIMMCs
- Any Treatment-Related AESIs: NOCMs
- Any Treatment-Related unsolicited AESIs: Serologically or Virologically Events Confirmed Relevant to COVID-19

All the categories above will be summarized by SOC and PT separately.

In addition, separate listings containing individual subject adverse event data for unsolicited AEs, unsolicited TEAEs leading to discontinuation from participation in the study or study treatment, serious AEs and unsolicited MAAEs will be provided separately.

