9.1.1.4. Adverse Events of Special Interest (AESI)

For this study, protocol specified AESIs are serologically or virologically confirmed SARS-CoV-2 infection or severe COVID-19. AESIs also include the Brighton Collaboration AESIs relevant to vaccination that are listed below:

- NOCMCs – defined as any new ICD diagnosis (per current International Statistical Classification of Diseases and Related Health Problems) that is applied to the subject during the course of the study, after receipt of the study agent, that is expected to continue for at least 3 months and requires continued health care intervention.
- MAAEs – defined as hospitalization, an emergency room visit or an otherwise unscheduled visit to or from medical personnel for any reason.
- PIMMCs – These constitute a group of AEs that includes diseases which are clearly autoimmune in etiology and other inflammatory and/or neurologic disorders which may or may not have autoimmune etiology. PIMMCs that are of special interest for this study are Brighton Collaboration AESIs relevant to vaccination that include: seizures, Guillain-Barre syndrome, acute disseminated encephalomyelitis, vasculitis, anaphylaxis, vaccine associated enhanced respiratory disease, thrombocytopenia, and thrombotic events.

All AESIs will be assessed, recorded, and followed as described above under AEs.

AESIs that meet SAE criteria will be reported on a SAE form within 24 hours of the site's awareness to the Gritstone/PPD Pharmacovigilance Group. In addition, for documentation and medical assessment purposes, AESIs that do not meet SAE criteria will also be reported on an SAE form within the period for AE reporting to the Gritstone/PPD Pharmacovigilance Group; however, the narrative will indicate that the AESI did not meet SAE criteria.

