- 15 In case of second dose delay (± 3), all safety visits (Visit 07 to Visit 12) will be scheduled based on the day of the second dose (e.g., Visit 07 will occur 1 day after delayed second dose and not on Day 30). All visits will shift based on the second dose without changing the time interval between 2 consecutive visits.
- 16 Cohorts 3 and 4 will complete Visit 13 (Day 394) if the visit window occurs prior to the last study participant completing Visit 12 (Day 209). Cohort 6 will not complete Visit 13 (Day 394).

Approved

Gritstone bio, Inc.
GO-009

Statistical Analysis Plan, Version 5.0
Date Issued: 09JUN2023

Appendix 2

Table 9 Planned Tables, Listings, and Figures (TLFs)

#	Type	Output #	Output Header	Population
1	Table	14.1.1.1	Subject Screening and Enrollment	All Screened Subjects Analysis Set
2	Table	14.1.1.2	Subjects Disposition and Analysis Sets	Intent-to-Treat Analysis Set*
3	Table	14.1.2.2	Major Protocol Deviations	Safety Analysis Set
4	Table	14.1.3	Demographics	Safety Analysis Set
5	Table	14.1.4	Medical History	Safety Analysis Set
6	Table	14.2.1	Analysis of Incidence Rate of COVID-19 Positive Tests	Safety Analysis Set
7	Table	14.3.1.1.1	Summary of Subjects with Solicited Adverse Events Within 8 Days After the Injection of Prime Dose by Maximum Grade	Safety Analysis Set
8	Table	14.3.1.1.2	Summary of Subjects with Solicited Adverse Events Within 8 Days After the Injection of Booster Dose by Maximum Grade	Safety Analysis Set
9	Table	14.3.1.2.1	Summary of Subjects with Solicited Adverse Events Within 8 Days After the Injection of Prime Dose by Maximum Grade and Onset Day	Safety Analysis Set
10	Table	14.3.1.2.2	Summary of Subjects with Solicited Adverse Events Within 8 Days After the Injection of Booster Dose by Maximum Grade and Onset Day	Safety Analysis Set
11	Table	14.3.1.3.1	Summary of Subjects with Solicited Adverse Events Within 8 Days After the Injection of Prime Dose by Onset Day	Safety Analysis Set
12	Table	14.3.1.3.2	Summary of Subjects with Solicited Adverse Events Within 8 Days After the Injection of Booster Dose by Onset Day	Safety Analysis Set

Gritstone bio, Inc.
GO-009Statistical Analysis Plan, Version 5.0
Date Issued: 09JUN2023

13	Table	14.3.1.4.1	Subject Incidence of Solicited Adverse Events by Term Related to the Injection of Prime Dose	Safety Analysis Set
14	Table	14.3.1.4.2	Subject Incidence of Solicited Adverse Events by Term Related to the Injection of Booster Dose	Safety Analysis Set

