43	Table	14.3.1.25	Subject Incidence of Unsolicited Treatment-Related Treatment-Emergent NOCMCs by System Organ Class and Preferred Term Throughout the Study	Safety Analysis Set
44	Table	14.3.4.1.1.1	Summary of Actu 1 Value and Change from Baseline in Hematology	Safety Analysis Set – Cohort 1 and 2 without Booster Dose
45	Table	14.3.4.1.1.2	Summary of Actual Value and Change from Baseline in Hematology	Safety Analysis Set – Cohort 1 and 2 with Booster Dose
46	Table	14.3.4.1.1.3	Summary of Actual Value and Change from Baseline in Hematology	Safety Analysis Set – Cohort 3, 4, and 6
47	Table	14.3.4.1.2.1	Summary of FDA Toxicity Grades for Hematology	Safety Analysis Set – Cohort 1 and 2 without Booster Dose
48	Table	14.3.4.1.2.2	Summary of FDA Toxicity Grades for Hematology	Safety Analysis Set – Cohort 1 and 2 with Booster Dose
49	Table	14.3.4.1.2.3	Summary of FDA Toxicity Grades for Hematology	Safety Analysis Set – Cohort 3, 4, and 6
50	Table	14.3.4.1.3.1	Shift from Baseline in Toxicity Grades for Hematology	Safety Analysis Set – Cohort 1 and 2 without Booster Dose

Gritstone bio, Inc.
GO-009

Statistical Analysis Plan, Version 5.0
Date Issued: 09JUN2023

51	Table	14.3.4.1.3.2	Shift from Baseline in Toxicity Grades for Hematology	Safety Analysis Set – Cohort 1 and 2 with Booster Dose
52	Table	14.3.4.1.3.3	Shift from Baseline in Toxicity Grades for Hematology	Safety Analysis Set – Cohort 3, 4, and 6
53	Table	14.3.4.2.1.1	Summary of Actual Value and Change from Baseline in Chemistry	Safety Analysis Set – Cohort 1 and 2 without Booster Dose
54	Table	14.3.4.2.1.2	Summary of Actual Value and Change from Baseline in Chemistry	Safety Analysis Set – Cohort 1 and 2 with Booster Dose
55	Table	14.3.4.2.1.3	Summary of Actual Value and Change from Baseline in Chemistry	Safety Analysis Set – Cohort 3, 4, and 6
56	Table	14.3.4.2.2.1	Summary of FDA Toxicity Grades for Chemistry	Safety Analysis Set – Cohort 1 and 2 without Booster Dose
57	Table	14.3.4.2.2.2	Summary of FDA Toxicity Grades for Chemistry	Safety Analysis Set – Cohort 1 and 2 with Booster Dose
58	Table	14.3.4.2.2.3	Summary of FDA Toxicity Grades for Chemistry	Safety Analysis Set – Cohort 3, 4, and 6
59	Table	14.3.4.2.3.1	Shift from Baseline in Toxicity Grades for Chemistry	Safety Analysis Set – Cohort 1 and 2 without Booster Dose
60	Table	14.3.4.2.3.2	Shift from Baseline in Toxicity Grades for Chemistry	Safety Analysis Set – Cohort 1 and 2 with Booster Dose

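### Whole-study SAE, MAAE, PIMMC and NOCMC tables use crude percentages of cohort N although planned follow-up runs from 7 to 16 months; person-time and first-event rates should be shown beside them

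*SAP*

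**What the plan says.** SAEs and AESIs (including PIMMCs, MAAEs and NOCMCs) over the whole study are the last primary endpoint (Protocol 3.1; SAP 2). SAP 9.1.1 provides for them in two ways. A 28-day overview after vaccination includes serious TEAEs and any unsolicited AESI. Then: "An overall summary of the following AEs will be presented throughout the entire study", with a list that includes SAEs, MAAEs, PIMMCs and NOCMCs. SAP 9.1 fixes the denominator: "Percentages will be based upon the number of participants in the Safety Analysis Set within each cohort". The matching outputs in SAP Appendix 2, Table 9 (14.3.1.12, 14.3.1.13, 14.3.1.16 to 14.3.1.25) are subject-incidence or summary tables over the study.

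Follow-up after the prime, from SAP 3.1 and Protocol 6.3:

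- **Cohorts 1 and 2:** 12 months without the booster, 16 months with it. These subjects began on a one-dose plan, and per SAP 7.2 "In order to receive a booster dose, each subject needed to sign another ICF".
- **Cohorts 3 and 4:** up to 13 months. Footnote 16 of SAP Table 8 says "Cohorts 3 and 4 will complete Visit 13 (Day 394) if the visit window occurs prior to the last study participant completing Visit 12", which is scheduled for Day 209.
- **Cohort 6:** 7 months, with no Visit 13.

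Time at risk is defined only for COVID-19 incidence, in SAP 8.1: "Person-Days at risk are defined as the total time from injection date of prime dose to the date of the positive PCR test", or the AE start date for the second COVID-19 measure, censored at the last date of participation or data cutoff.

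**The concern.** A percentage of subjects with at least one event grows with the time over which events are counted. MAAEs show this most clearly, because the definition takes in "an otherwise unscheduled visit to or from medical personnel for any reason" (SAP 9.1.1.4), so they accumulate whatever the vaccine does. A reader who sees the cohort columns side by side has no time base for any of them.

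A Cohort 1 or 2 column may also pool 12-month and 16-month subjects. Table 9 separates laboratory and vital-sign tables by booster status, with populations such as "Cohort 1 and 2 with Booster Dose", but the whole-study AE tables carry no such split.

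At stake is the reading of a primary safety estimate. Part of a difference between cohorts could come from length of observation alone.

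**Working it through.** **The plan's own figure.** SAP 4.3 gives an 89% chance of at least one event in 10 subjects at a true rate of 20%. This reproduces: 1 − 0.8^10 = 0.8926. The figure has no time unit, and the documents state no event rate per unit of time.

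**Inputs.** Last visit days from the schedules: Day 209 (Cohort 6, Visit 12), Day 365 (Cohorts 1/2 unboosted), Day 478 (Cohorts 1/2 boosted), Day 394 (Cohorts 3/4, Visit 13 if held). N = 10 per cohort. Assumptions: equal constant hazard h in all cohorts, no early withdrawal, and the visit day taken as length of follow-up.

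**Formula.** Expected percentage with at least one event by day d: p(d) = 1 − exp(−h × d/365.25).

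| h per 100 person-years | Day 209 | Day 365 | Day 394 | Day 478 |
|---|---|---|---|---|
| 5 | 2.82% | 4.87% | 5.25% | 6.33% |
| 10 | 5.56% | 9.51% | 10.23% | 12.27% |
| 20 | 10.81% | 18.12% | 19.41% | 23.03% |
| 50 | 24.88% | 39.33% | 41.69% | 48.02% |

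**Cohort 1 or 2 against Cohort 6** (ratio to p(209)):

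| h | none boosted | half boosted | all boosted |
|---|---|---|---|
| 5 | 1.73 | 1.99 | 2.25 |
| 10 | 1.71 | 1.96 | 2.21 |
| 20 | 1.68 | 1.90 | 2.13 |
| 50 | 1.58 | 1.76 | 1.93 |
| 100 | 1.45 | 1.56 | 1.67 |

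**Expected subjects per 10**, half-boosted Cohort 1 or 2 against Cohort 6: 0.6 v 0.3 at h = 5; 2.1 v 1.1 at 20; 4.4 v 2.5 at 50.

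**Chance that the half-boosted cohort shows the higher count** at equal hazard (binomial, 10 subjects each): 35% at h = 5 (with a 50% chance of a tie), 49% at 10, 61% at 20, 75% at 50.

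**Cohort 4 against Cohort 6.** Over h = 5 to 50 the ratio is 1.0 if no Cohort 4 subject reaches Visit 13, 1.34 to 1.43 if half do, and 1.68 to 1.86 if all do. On nominal days, the earliest Visit 13 (394 − 7 = Day 387) falls before the last participant's Visit 12 only if the subject's prime came at least 387 − 209 = 178 days before that participant's. Protocol 12.3.1 says "Cohorts 3, 4, and 6 will be enrolled in parallel", and the accrual span is not given, so the share cannot be derived.

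**What a rate changes.** Person-years for 10 subjects over full planned follow-up: 10 × 209/365.25 = 5.72 and 10 × 478/365.25 = 13.09. Take 2/10 in a fully boosted cohort and 1/10 in Cohort 6. The crude table reads 20% v 10%. Per 100 person-years this is 2/13.09 = 15.3 (exact Poisson 95% CI 1.9 to 55.2) v 1/5.72 = 17.5 (0.4 to 97.4). Censoring at the first event, as SAP 8.1 does, would shorten both denominators somewhat.

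**Do the dose-period tables equalise time?** SAP 9 and 9.1 also present safety by prime and booster period. Nominally, the pre-booster period is 112 days in boosted Cohorts 1/2 (Day 1 to 113) and 28 days in Cohorts 3, 4 and 6 (Day 1 to 29). The post-booster period is 478 − 113 = 365 days in boosted Cohorts 1/2 and 209 − 29 = 180 in Cohort 6. They do not.

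**The case against.** The strongest reply is that the comparison in question is not a planned one. Protocol 12.1 rules out hypothesis tests between cohorts, and nothing is randomised. Cohorts 1 and 2 also differ from Cohort 6 in age, prior vaccine and boost interval, and Cohort 2 in dose as well. Person-time would not make those columns comparable. This stands, and it limits the point to descriptive reading. It does not remove it: Protocol 12.1 also says the aim is to obtain preliminary safety estimates, and a percentage without a time base is a weak estimate even for one cohort.

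Three stronger readings are tempting, and the documents do not support them.

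- A reader might infer that crude whole-study percentages are all the plan offers. Protocol 12.4.2 describes SAEs through detailed listings with dates, SAP 9.1.1 adds SAE and MAAE listings, the 28-day overview uses an equal window, and treatment-related tables are planned. With 10 subjects per cohort these are substantive displays. They trace events or cover a short window, however, and give no time at risk for the whole-study endpoint.
- A reader might infer that the percentages will rank cohorts by length of follow-up. For uncommon events that is too strong: at 5 per 100 person-years a tie is the likeliest result.
- A reader might see a conflict over Cohort 6 in the SAP 3.1 end-of-study sentence. It can be read as a ceiling of 12 months, which is compatible with 7. It is a separate wording point and adds no weight here.

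**Conclusion.** The point holds as a cheap improvement worth considering. The whole-study tables for a primary safety endpoint use a fixed-N denominator over planned follow-up that differs more than twofold (478/209 = 2.29), and no other planned summary corrects for that.

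The size rests on an assumption the documents do not supply: an equal constant hazard of 5 to 50 first events per 100 person-years, with full follow-up. Under it, the expected Cohort 1 or 2 percentage is about 1.6 to 2.2 times that of Cohort 6, the position in the range depending on the hazard and on how many subjects are boosted. At 100 per 100 person-years it falls to 1.45 to 1.67, so very frequent MAAEs could lie below the headline range. For rare classes the absolute gap is a fraction of a subject per 10.

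Cohort 4 v Cohort 6 shares dose, prior vaccine type and boost interval and differs in age. Its ratio may be anywhere from 1.0 to about 1.9, so a distortion there cannot be presumed. No test, decision rule or 28-day summary is affected.

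**What to change.** In SAP 9.1.1, keep the crude tables and show total person-time per cohort beside them. For SAEs, MAAEs, PIMMCs and NOCMCs, add the number of subjects with a first event per 100 person-years with exact Poisson 95% CIs. Use the time at risk of SAP 8.1: from the prime dose to the first event of that class, the last date of study participation or the data cutoff, whichever is earliest. COVID-19 is already covered there.

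Optionally add counts and percentages from Dose 1 through Day 209. A footnote should say that this equalises time since the prime, not post-boost exposure. By Day 209, boosted Cohort 1/2 subjects have 75 to 99 post-boost days (nominally 209 − 113 = 96; the −3/+21 day window puts the boost between Day 110 and Day 134). Unboosted subjects have none, and Cohorts 3, 4 and 6 have about 180. Early withdrawals still have shorter follow-up.

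The cost is some SAP wording and a few tables from dates already collected. There are two downsides. The intervals will be wide, as the single-event example shows. Person-year rates also dilute events clustered soon after dosing, which the planned 28-day summaries show better, so the rates should supplement those summaries and not replace them.

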Follow-up Duration	For Cohorts 1 and 2 (NOT receiving booster dose): 12 months For Cohorts 1 and 2 (receiving booster dose): 16 months For Cohorts 3 and 4: up to 13 months For Cohort 6: 7 months
Primary Objectives	
• To assess the safety and tolerability of 2 different doses (10 or 30 mcg) of GRT-R910 when administered to healthy adults (≥ 60 years of age) who were previously vaccinated with a first-generation Coronavirus Disease 2019 (COVID-19) vaccine (Cohorts 1 and 2; AstraZeneca)• To assess the safety and tolerability of a 10 mcg dose of GRT-R910 when administered to healthy adults (≥ 18 years of age) who were previously vaccinated with an mRNA-based COVID-19 vaccine (Pfizer/BioNTech, Moderna)

Primary Outcome Measures	
Occurrence of solicited local reactogenicity signs and symptoms for 7 days after GRT-R910 vaccinationOccurrence of solicited systemic reactogenicity signs and symptoms for 7 days after GRT-R910 vaccinationOccurrence of unsolicited adverse events (AEs) for 28 days after last study-administered GRT-R910 vaccinationChange from baseline for clinical safety laboratory parameters 7 days after last study-administered GRT-R910 vaccinationOccurrence of serious adverse events (SAEs) and adverse events of special interest (AESIs), including potentially immune-mediated medical conditions (PIMMCs), medically attended adverse events (MAAEs), and new onset chronic medical conditions (NOCMCs), throughout the entire study after GRT-R910 vaccination
Secondary Objective	
To assess the cellular and humoral immunogenicity of GRT-R910 when administered to volunteers (≥ 60 years of age for Cohorts 1, 2, 3, and 4 and ≥ 18 to ≤ 59 years of age for Cohort 6) who were previously vaccinated with either an adenoviral COVID-19 vaccine (AstraZeneca, Janssen) or an mRNA-based COVID-19 vaccine (Pfizer/BioNTech, Moderna)
Secondary Outcome Measures	
Response rate, and magnitude of SARS-CoV-2-specific antibody binding and neutralization in serum samplesResponse rate, magnitude, and breadth of SARS-CoV-2 specific T-cells as assessed by interferon (IFN)-γ enzyme-linked immunospot (ELISpot) in 10 subjects per cohort
	[REDACTED]

Rationale

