11.1.1.2 Unsolicited Adverse Events

Unsolicited non-serious AEs will be captured for 28 days following each GRT-R910 vaccination. In addition, AESIs, including PIMMCs, MAAEs, and NOCMCs, will be captured throughout the entire study following GRT-R910 vaccination.

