11.1.5 Adverse Events of Special Interest (AESIs)

An adverse event of special interest (serious or nonserious) is one of scientific and medical concern specific to the sponsor's product or program, for which ongoing monitoring and rapid communication by the investigator to the sponsor can be appropriate. Such an event might warrant further investigation in order to characterize and understand it. Depending on the nature of the event, rapid communication by the trial sponsor to other parties (e.g., regulators) might also be warranted. For this study, protocol-specified AESIs are serologically or virologically confirmed SARS-CoV-2 infection or severe COVID-19. AESIs also include the Brighton Collaboration AESIs relevant to vaccination that are listed below:

- NOCMCs – defined as any new ICD diagnosis (per current International Statistical Classification of Diseases and Related Health Problems) that is applied to the subject during the course of the study, after receipt of the study agent, that is expected to continue for at least 3 months and requires continued health care intervention.
- MAAEs – defined as hospitalization, an emergency room visit or an otherwise unscheduled visit to or from medical personnel for any reason.
- PIMMCs – These constitute a group of AEs that includes diseases which are clearly autoimmune in etiology and other inflammatory and/or neurologic disorders which may or may not have autoimmune etiology. PIMMCs that are of special interest for this study

are Brighton Collaboration AESIs relevant to vaccination that include: seizures, Guillain-Barre syndrome, acute disseminated encephalomyelitis, vasculitis, anaphylaxis, vaccine-associated enhanced respiratory disease, thrombocytopenia, and thrombotic events.

All AESIs are assessed, recorded, and followed as described above under AEs.

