30	Table	14.3.1.14.1	Subject Incidence of Unsolicited Severe TEAEs by System Organ Class and Preferred Term up to 28 Days After the Injection of Prime Dose	Safety Analysis Set
31	Table	14.3.1.14.2	Subject Incidence of Unsolicited Severe TEAEs by System Organ Class and Preferred Term up to 28 Days After the Injection of Booster Dose	Safety Analysis Set

Gritstone bio, Inc.
GO-009Statistical Analysis Plan, Version 5.0
Date Issued: 09JUN2023

32	Table	14.3.1.15.1	Subject Incidence of Unsolicited Severe Treatment-Related TEAEs by System Organ Class and Preferred Term up to 28 Days After the Injection of Prime Dose	Safety Analysis Set
33	Table	14.3.1.15.2	Subject Incidence of Unsolicited Severe Treatment-Related TEAEs by System Organ Class and Preferred Term up to 28 Days After the Injection of Booster Dose	Safety Analysis Set
34	Table	14.3.1.16	Summary of Unsolicited TEAEs of Special Interest Throughout the Study	Safety Analysis Set
35	Table	14.3.1.17	Subject Incidence of Unsolicited TEAEs of Special Interest by System Organ Class and Preferred Term Throughout the Study	Safety Analysis Set
36	Table	14.3.1.18	Subject Incidence of Unsolicited Treatment-Emergent MAAEs by System Organ Class and Preferred Term Throughout the Study	Safety Analysis Set
37	Table	14.3.1.19	Subject Incidence of Unsolicited Treatment-Emergent Severe COVID-19 by System Organ Class and Preferred Term Throughout the Study	Safety Analysis Set
38	Table	14.3.1.20	Subject Incidence of Unsolicited Treatment-Emergent PIMMCs by System Organ Class and Preferred Term Throughout the Study	Safety Analysis Set
39	Table	14.3.1.21	Subject Incidence of Unsolicited Treatment-Emergent NOCMs by System Organ Class and Preferred Term Throughout the Study	Safety Analysis Set
40	Table	14.3.1.22	Subject Incidence of Unsolicited Treatment-Emergent Serologically or Virologically Events Confirmed Relevant to COVID-19 by System Organ Class and Preferred Term Throughout the Study	Safety Analysis Set

Gritstone bio, Inc.
GO-009

Statistical Analysis Plan, Version 5.0
Date Issued: 09JUN2023

41	Table	14.3.1.23	Subject Incidence of Unsolicited Treatment-Related Treatment-Emergent MAAEs by System Organ Class and Preferred Term Throughout the Study	Safety Analysis Set
42	Table	14.3.1.24	Subject Incidence of Unsolicited Treatment-Related Treatment-Emergent PIMMCs by System Organ Class and Preferred Term Throughout the Study	Safety Analysis Set

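### The SAP restricts its MAAE summary row, listing and tables to unsolicited events, so a non-serious solicited reaction that leads to a medical visit is left out of the MAAE component of a primary outcome

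*SAP*

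**What the plan says.** **Definition.** Protocol 11.1.5 gives MAAEs as "defined as hospitalization, an emergency room visit or an otherwise unscheduled visit to or from medical personnel for any reason". SAP 9.1.1.4 repeats this definition. Neither document exempts solicited reactions.

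**Endpoint.** The last primary outcome in Protocol 3.1 covers SAEs and AESIs, including "medically attended adverse events (MAAEs), and new onset chronic medical conditions (NOCMCs), throughout the entire study after GRT-R910 vaccination". SAP section 2 carries the same outcome.

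**Planned MAAE outputs.** In SAP 9.1.1 the all-MAAE row for the entire study reads "Any unsolicited medically attended TEAEs (MAAEs"), and the listing sentence ends "serious AEs and unsolicited MAAEs will be provided separately". In SAP Appendix 2, Table 9, row 36 (output 14.3.1.18) is "Subject Incidence of Unsolicited Treatment-Emergent MAAEs by System Organ Class and Preferred Term Throughout the Study". Row 41 (14.3.1.23), the treatment-related counterpart, is also titled as unsolicited, as are the AESI tables in rows 34 and 35. The whole-study list in 9.1.1 nevertheless includes "Any Treatment-Related MAAEs" with no restriction.

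**Which reactions become unsolicited.** SAP 9.1.2 moves a reaction out of the solicited class in two cases only: it fits none of the solicited categories, or it is serious.

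**The concern.** Whether an event is solicited or unsolicited depends on the symptom and its collection window. Whether it is medically attended depends on what the subject did about it. The two classifications cross, but the SAP treats the second as a subset of unsolicited events. Fever or myalgia two days after the injection that sends a subject to a doctor, without meeting a seriousness criterion, is an MAAE by definition and solicited by type. The all-MAAE row, the listing and rows 36 and 41 then pass over it.

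The solicited outputs do not make up for this. SAP 9.1.2 and Table 9 rows 7 to 18 describe incidence, grade, onset day, duration and persistence past the window, but give no count of subjects who sought care. At stake is the accuracy of one safety component of a primary outcome in a study whose purpose is to characterize safety. The solicited terms are those the plan itself regards as anticipated after vaccination, so the filter acts on a class of event that matters for tolerability.

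**Working it through.** **Step 1. Follow one event through the plan.** Take a non-serious Grade 2 fever on Day 3 after the prime dose, judged related, with an unscheduled doctor's visit and no other MAAE in that subject.

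| Place in the plan | Is the subject counted? |
|---|---|
| MAAE definition (Protocol 11.1.5, SAP 9.1.1.4) | Yes |
| Primary SAE/AESI outcome (Protocol 3.1, SAP section 2) | Yes |
| Reclassified as unsolicited (SAP 9.1.2) | No: a listed term, not serious |
| All-MAAE row, SAP 9.1.1 | No |
| MAAE listing, SAP 9.1.1 | No |
| Treatment-related MAAE row, SAP 9.1.1 | Yes, read literally |
| Table 9 row 36 (14.3.1.18) | No |
| Table 9 row 41 (14.3.1.23) | No |
| Solicited tables, rows 7 to 16, and listings, rows 98 and 99 | Yes, without a medically attended count |

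This subject is in the treatment-related MAAE row and absent from the all-MAAE row, so a subset can exceed the set it belongs to. The same treatment-related category is unrestricted in 9.1.1 and restricted in row 41.

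**Step 2. Direction.** The filter can only remove subjects. A subject drops out of the count when every MAAE that he or she has is a non-serious solicited reaction; otherwise the count is unchanged. The error is zero or downward.

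**Step 3. The plan's own figure.** Protocol Table 5 and SAP Table 3 use P(at least one event) = 1 − (1 − p)^n. For n = 10 and p = 0.20, 1 − 0.80^10 = 89.26%, as printed. All 21 cells reproduce. This point changes none of them, but the same formula is used in step 5.

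**Step 4. Effect of one omitted subject.** The intervals are exact Clopper-Pearson, the SAP default (section 4.2). For 0 of n the upper limit is 1 − 0.025^(1/n). For 1 of n the lower limit is 1 − 0.975^(1/n), and the upper limit is the 97.5% point of a Beta(2, n − 1) distribution.

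| Denominator | Solicited MAAE excluded | Solicited MAAE included |
|---|---|---|
| One cohort, n = 10 | 0/10 = 0% (0 to 30.8%) | 1/10 = 10% (0.25 to 44.5%) |
| Whole study, n = 50 | 0/50 = 0% (0 to 7.1%) | 1/50 = 2% (0.1 to 10.6%) |

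**Step 5. How likely an omission is.** Neither document states how often subjects seek care for a reaction, so the rate p is an assumption: the probability that a subject has at least one non-serious, medically attended solicited reaction across the doses received. With 50 independent subjects:

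| Assumed p | Expected subjects, 50p | P(at least one), 1 − (1 − p)^50 |
|---|---|---|
| 1% | 0.5 | 39.5% |
| 2% | 1 | 63.6% |
| 5% | 2.5 | 92.3% |
| 10% | 5 | 99.5% |

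**The case against.** **The protocol files MAAEs under unsolicited events.** Protocol 11.1.1.2, headed as unsolicited, says "In addition, AESIs, including PIMMCs, MAAEs, and NOCMCs, will be captured throughout the entire study following GRT-R910 vaccination", and the SAP label may simply follow that placement. This stands to the extent that the matter is not a clean departure of the SAP from the protocol. But that sentence fixes how long AESIs are captured. It does not narrow the definition in 11.1.5 or the outcome in 3.1, and the SAP repeats the broad definition. Section 11 of the SAP does not declare a restriction.

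**Serious reactions are already covered.** Correct. SAP 9.1.2 summarizes a serious reaction as a serious unsolicited event, so one that causes inpatient hospitalization can enter row 36. A reader might infer that hospitalized reactions are lost too; the documents do not support that.

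**The event is not lost.** Also correct. It counts in the solicited primary outcomes, appears in their tables and listings, and, as an AESI, is to be reported on an SAE form even when non-serious (Protocol 11.2.1). A reader might infer that it vanishes from the primary endpoints. It does not. What is missing is its count as an MAAE, which the solicited outputs do not supply.

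**The treatment-related row is open.** In the text of 9.1.1 it is, so exclusion of related MAAEs is not uniform. Row 41 contradicts that row, and the contradiction is itself a defect.

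**The numbers are small and nothing is tested.** True: Protocol 12.1 plans no hypothesis test, and the intervals in step 4 overlap heavily. The case for change is that the count should match its definition.

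**Conclusion.** The point holds for non-serious reactions within the solicited terms that prompt an emergency room or unscheduled visit. As written, the SAP leaves them out of the all-MAAE row, the MAAE listing and Table 9 rows 36 and 41, against its own definition, and its treatment-related row conflicts with row 41. The MAAE component of the primary SAE/AESI outcome can only be understated: by 10 percentage points in a cohort of 10, or 2 points in 50, for each subject whose only MAAE is of this kind.

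How many subjects that would be is unknown. The probabilities of 39.5% to 99.5% rest on assumed rates of 1% to 10%, full enrolment of 50 and independence between subjects. A reader might go further and infer that most treatment-related MAAEs would be missed, or that what remains is largely background illness. The documents give no rate of care-seeking and no split of MAAEs by cause, so neither inference is supported.

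One limit on the evidence: Table 9 was available only through row 107 and no MAAE listing title appears there, so the statement about the listing rests on the text of SAP 9.1.1.

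**What to change.** In SAP 9.1.1, delete the word unsolicited from the all-MAAE row and from the MAAE listing. Do the same in the titles and filters of Table 9 rows 36 and 41, and for MAAEs within rows 34 and 35. Count all MAAEs and show those arising from solicited reactions on a separate line, so that the unsolicited figure remains visible. This brings row 41 into line with the treatment-related row in the text and removes the possibility that the subset exceeds the total.

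If the sponsor means to keep the restriction, the least that is needed is to reconcile row 41 with 9.1.1 and declare the narrower MAAE count in SAP section 11.

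The cost is SAP wording and a wider filter on the affected tables and one listing. The source record should exist, because AESIs are reported on an SAE form whether or not they are serious. The one downside is that the reported MAAE rate may look slightly less favourable.
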